#### 8.1.4. Severity

The investigator must define the severity of each AE using the following definitions as a guideline. The investigator will consider the range of the possible severity of the event and identify the severity that is the most appropriate according to her/his medical judgment.

**Mild** – Awareness of signs or symptom, but easily tolerated.

**Moderate** – Discomfort, enough to cause interference with usual activity.

**Severe** – Incapacitating with inability to perform usual activity.

#### 8.1.5. Relationship to study medication

The investigator will determine if there is a reasonable causal relationship between the study medication and an AE or not. The investigator will use her/his best medical judgment and consider all relevant factors (e.g., temporal relationship, location of the event, the subject's relevant medical history, concomitant therapies and concurrent conditions) to determine the relationship of the AE to the study medication. The investigator will define the relationship of an AE to the study medication by selecting one of the following categories:

**Related** – There is a reasonable possibility that there is a causal relationship between the study medication and the AE.

**Not Related** – There is not a reasonable possibility that there is a causal relationship between the study medication and the AE.

The term “reasonable causal relationship” means there are facts or arguments to suggest a causal relationship (International Conference on Harmonization (ICH) E2A).

### 8.2. Reporting Procedures

#### 8.2.1. Procedures for reporting adverse events

At each post randomization visit (Visit 2), the investigator or designee will question the subject to elicit AEs using a non-directive question such as “Has there been any change in your health since the previous study visit?”

At Visit 2, the investigator or designee will monitor the subject for at least 20 minutes after the first study medication application at Visit 2 to elicit AEs in a similar manner.

If appropriate, based on the subject's response to non-directed questioning regarding AEs, the investigator or designee will follow-up with directed questions and appropriate evaluations.

Any AE noted during the reporting period must be reported in the source documents and on the appropriate AE eCRF.

AEs that are defined as “Not Related” to the study medications will be followed until they are resolved or until the subject’s last study visit. AEs that are defined as “Related” to the study medications will be followed until they are resolved or, if not resolved after the subject’s last study visit, until in the opinion of the investigator, the AE reaches a clinically stable outcome with or without sequelae.

### **8.2.2. Procedure for reporting a serious adverse event**

Upon becoming aware of a SAE occurring during the AE reporting period, whether or not related to the study medication, the investigator must:

1. Take the appropriate medical action to ensure the subject’s safety.
2. Immediately inform the Safety Monitor of the SAE by email, ensuring that the subject information is deidentified (only subject initials and subject number) to:
  - **ProPharma, Email:** [[contact]](mailto:[contact])
  - **[contact]**
3. Print a copy of the email confirmation from ProPharma and place in the study file.
4. Within 24-hours complete, as fully as possible, an AE eCRF and an SAE form; e-mail the forms and any other relevant information (e.g., concomitant medication eCRF, medical history eCRF, laboratory test results) to ProPharma (Aclaris Therapeutics, Inc. Safety Monitor).
5. Monitor and document the progress of the SAE until it resolves or, if not resolved after the subject’s last study visit, until in the opinion of the investigator the AE reaches a clinically stable outcome with or without sequelae AND the investigator and Aclaris Therapeutics, Inc. Safety and Medical Monitor agree that the SAE is satisfactorily resolved.
6. Inform the Aclaris Therapeutics, Inc. Safety Monitor of SAE updates, via telephone, followed by an SAE form update sent by e-mail.
7. Comply with the appropriate regulatory requirements and Aclaris Therapeutics, Inc. instructions regarding reporting of the SAE to the responsible Institutional Review Board (IRB) or Ethics Committee (EC).

### **8.2.3. Safety Monitoring ECG Discontinuation Criteria**

Any subject who develops any of the following ECG criteria during the active treatment phase will be instructed to stop study medication and will be withdrawn from the study:

- A post-study medication ECG result where the evaluator’s interpretation shows any of the following:
  - Clinically significant rhythm disturbance other than sinus rhythm or ectopic supraventricular rhythm (ectopic atrial rhythm)
  - Clinically significant conduction disturbance including PR >240msec, pre-excitation (delta wave and PR <120msec), second degree or higher AV block

CONFIDENTIAL  
Page 45 of 57

- New finding of QRS>120ms (if not present at screen. For example, subjects with Right Bundle Branch Block at screening would not need to be withdrawn from the study if their subsequent ECGs remained unchanged)
- Evidence of QT-interval prolongation, defined as an increase in the QTcF interval >60ms from Visit 1
- New QTcF > 500 ms
- Acute signs of ischemia or infarction
- Any ECG abnormality which may, in the opinion of the investigator, represent a new medical issue of concern

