**Study Design:**

This is an open-label study which will be conducted at 1 to 2 sites.

Subjects will be required to have a clinical diagnosis of AA, AU or AT with unilateral or bilateral loss of eyebrow hair with a duration of the current episode of at least 6 months, but not more than seven years. A total of approximately 12 subjects will apply ATI-50002 Topical Solution 0.46%, to the affected eyebrow(s) twice-daily (BID) for 24 weeks.

After completing Visit 1 (start of the screening period), subjects will be assessed for eligibility to receive study medication.

Subjects will apply study medication to the entire affected eyebrow(s), twice-daily for 24 weeks. The 24-week treatment period will be followed by a 4-week no-treatment follow-up period. Assessment of response to treatment will be performed at Week 4, Week 8, Week 12, Week 16, Week 20, Week 24 and Week 28.

Safety and tolerability will be evaluated throughout the study by assessment of electrocardiograms (ECG), clinical laboratory tests, adverse events and vital signs.

The duration of the study participation is anticipated to be a maximum of 233 days (an up to 28-day screening period, a 169-day treatment period with a 4-day window, a 28-day no-treatment follow-up period with a window of 4 days).

Study visits are:

- Visit 1 (Day -28 to 0): screening; start eligibility assessment period
- Visit 2 (Week 0): initiation of twice-daily study medication application

CONFIDENTIAL

Page 7 of 57

- Visits 3-10 (Weeks 1-24): treatment period
- Visit 11 (Week 28): no-treatment period follow-up; end of study

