10. Discharge from the study subjects who are not eligible to apply the first dose of study medication.

For subjects who are eligible to apply the first dose of study medication the investigator or designee will perform the following procedures:

1. Have the subject complete a SEA; a SEA grade of 0 in a distinct patch with at least 30% total unilateral eyebrow hair loss is required for the subject to apply the first dose of study medication. Note: Subject may have multiple patches of eyebrow hair loss, but at least one distinct patch must demonstrate a minimum hair loss of at least 30% (independent of any other patches).
2. Have the subject complete the SES question.
3. Have the subject perform a pre-application Local Tolerability Assessment (LTA).
4. The Investigator or designee will perform a pre-application LTA.
5. Take standardized color photographs.
6. Conduct an ECG.
7. Dispense study medication to the subject.
8. An investigational staff member will instruct the subject on the proper study medication application technique and will observe the subject's first study medication application.
9. A staff member will monitor the subject for at least 20 minutes after the first study medication application completion time to detect any adverse events.
10. Have the subject perform a post-application LTA 10 ( $\pm 4$ ) minutes after the application completion time.
11. The investigator or designee will perform a post-application LTA 20 ( $\pm 4$ ) minutes after the application completion time.
12. Review the study instructions with the subject.
13. Schedule Visit 3 as appropriate.

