#### **6.3.4. Visit 10 (Week 24)**

This visit must occur 24 weeks ( $\pm 4$  days) after Visit 2.

At this visit, the investigator or designee will perform the following procedures:

1. Query the subject in a non-directive manner about any changes in her/his health since the previous visit and report all AEs on the appropriate form.
2. Query the subject about any changes in her/his concomitant therapies since the previous visit and report changes on the appropriate form.
3. Confirm the subject continues to comply with all study restrictions and has followed all study instructions.
4. Measure vital signs.
5. Conduct an ECG.
6. Confirm subject had clinical laboratory tests prior to the visit (on the same day).
7. Perform a urine pregnancy test for WOCBP.
8. Have the subject perform a LTA.
9. The investigator or designee will perform a LTA.
10. The investigator or designee will perform the CEA.
11. Have the subject complete the SEA.
12. Have the subject complete the SES.
13. Collect all study medication.
14. Take standardized photographs.
15. Review the study instructions with the subject.
16. Schedule the next visit as appropriate.

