#### **6.3.5. Visit 11 (Week 28)**

This visit must occur 28 weeks ( $\pm 4$  days) after Visit 2.

At this visit, the investigator or designee will perform the following procedures:

1. Query the subject in a non-directive manner about any changes in her/his health since the previous visit and report all AEs on the appropriate form.
2. Query the subject about any changes in her/his concomitant therapies since the previous visit and report changes on the appropriate form.
3. Confirm the subject continues to comply with all study restrictions and has followed all study instructions.

4. Conduct a brief physical examination.
5. Measure vital signs.
6. Conduct an ECG.
7. Confirm subject had clinical laboratory tests prior to visit (same day).
8. Perform a urine pregnancy test for WOCBP.
9. Have the subject perform a LTA.
10. The investigator or designee will perform a LTA.
11. The investigator or designee will perform the CEA.
12. Have the subject complete the SEA.
13. Have the subject complete the SES.
14. Take standardized photographs.
15. Discharge the subject from the study.

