#### 7.2.1. ECGs

At Visits 1, 2, 10 and 11 a standard 12-lead ECG will be performed by a qualified staff member. The ECGs must be obtained using a standard 12-lead ECG with a 10mm/mV amplitude, at 25mm/sec and a 5-10-second duration. To ensure a steady heart rate the subject must rest quietly in the supine position for at least 5 minutes prior to performing the ECG.

A central lab will provide equipment, supplies and site training. In addition, the central lab will process the ECGs received by the sites and report results via a secure study portal. The ECG results will be interpreted by a qualified health professional (evaluator) and the interpretation reported either directly on the tracing or in a separate report. The evaluator will interpret the results of every ECG and define the ECG as “normal” or “abnormal”. Variations such as minor ST changes (*i.e.*, <0.5mm depression) and early re-polarization are considered normal.

The investigator must review the evaluator’s interpretation of each subject’s Visit 1 ECG prior to Visit 2. The investigator will review the evaluator’s interpretation of all ECG reports in a timely manner and comment on the clinical significance of any result that is defined by the evaluator as abnormal.

Any abnormalities that are, in the opinion of the investigator, CS must be reported as medical history if found prior to the start of the first study medication application or as an AE if found after the start of the first study medication application.

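### Section 8.2.3 ties stopping drug to leaving the study; on scheduled ECGs this only withdraws a flagged subject before the one scheduled off-drug ECG, at Week 28

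*Combined protocol and SAP*

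**What the plan says.** Section 8.2.3 lists ECG criteria, assessed on tracings taken after dosing has begun. A subject who develops one of them in the active treatment phase "will be instructed to stop study medication and will be withdrawn from the study". The two consequences form one action.

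Section 7.2.1 sets the schedule: "At Visits 1, 2, 10 and 11 a standard 12-lead ECG will be performed by a qualified staff member". It also provides for central reading: "the central lab will process the ECGs received by the sites and report results via a secure study portal".

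The synopsis places the visits: "Visits 3-10 (Weeks 1-24): treatment period" and "Visit 11 (Week 28): no-treatment period follow-up; end of study". The procedure list for Visit 10 (6.3.4) includes "Collect all study medication", with no condition attached. The list for Visit 11 (6.3.5) includes "Conduct an ECG".

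Several other provisions bear on a subject withdrawn in this way:

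- Section 5.6 asks the site to try to complete the last-day assessments after early discontinuation, and sends ongoing adverse events (AEs) in withdrawn subjects to follow-up under 8.2.1.
- Section 7.2.1 makes an ECG abnormality found after first application a reportable AE if the investigator judges it clinically significant.
- Section 8.2.1 follows related AEs to resolution or a stable outcome, and unrelated ones to resolution or the last study visit.
- Section 7.2 has an independent safety monitor review the data at least monthly.

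**The concern.** A stopping rule on ECG findings is meant to protect the subject by ending exposure. Here the only scheduled tracing that can set it off is taken at the visit where exposure ends for everyone. What the rule then adds is withdrawal, and that comes just before the visit carrying the only scheduled ECG off drug.

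Safety is part of the main objective (Section 4). If a subject shows a QTcF or QRS change at the end of treatment, a later off-drug tracing is the natural evidence on whether the change reverses. As written, every other subject who completes treatment has that tracing as a scheduled procedure, while the subject for whom it is most informative does not. Withdrawal also puts that subject's other Week 28 data at risk: laboratory tests, vital signs, local tolerability and the eyebrow scales.

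**Working it through.** The plan gives no figure to reproduce on this point. The check is a comparison of sections, with some day arithmetic.

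**1. Which scheduled ECGs can trigger the rule.** The tracing must be post-dose and in the treatment phase.

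| Visit | Position | Can trigger? |
|---|---|---|
| 1 | Screening, before any drug | No |
| 2 | ECG is item 6 of the eligible-subject list in 6.3.2; item 7 is "Dispense study medication to the subject" and item 8 the first application | No |
| 10 | Week 24, last visit of the treatment period in the synopsis | Yes |
| 11 | Week 28, no-treatment follow-up | No |

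The list for Visits 3 to 9 (6.3.3) contains no ECG. The count is 1 of 4.

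**2. What the rule changes at Visit 10.** Drug is collected from every subject at that visit, so the instruction to stop changes nothing. The instruction to withdraw removes the subject before Visit 11.

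**3. The gap to the off-drug tracing.** Visit 10 is 24 × 7 = 168 days after Visit 2 and Visit 11 is 28 × 7 = 196 days after it, each ±4 days.

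- Nominal: 196 − 168 = 28 days.
- Shortest: 192 − 172 = 20 days.
- Longest: 200 − 164 = 36 days.

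Section 3.1 gives a half-life of about 9.0 hours after the oral prodrug; applying it to topical use is an assumption. On that basis 28 days is 28 × 24 / 9 ≈ 75 half-lives (53 to 96 over the window), so Week 28 is clearly off drug.

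**4. Whether other text secures an off-drug ECG.**

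- *5.6, last-day assessments.* Section 6.5 identifies Visit 11 as the final visit, and its list includes an ECG. The clause asks for efforts and sets no date, so the assessments could be done on the day of Visit 10.
- *7.2.1, AE reporting.* It depends on a judgement of clinical significance. Three triggers in 8.2.3 carry no such qualifier: new QRS above 120 ms, QTcF increase above 60 ms, and new QTcF above 500 ms. The broad AE definition in 8.1.1 may capture these, but it calls for no tracing.
- *5.6 with 8.2.1, AE follow-up.* It is mandatory, and for related events it runs past the last visit. No repeat ECG is named. For unrelated events it ends at the last study visit at the latest, which withdrawal can bring forward.
- *7.2, monthly review.* It examines data already collected.

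**5. Size.** One subject is 1/12 = 8.3% of the planned sample. The documents give no trigger rate. For an assumed per-subject rate p, the chance of at least one trigger among 12 is 1 − (1 − p)^12:

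| Assumed p | Chance of at least one trigger |
|---|---|
| 1% | 11% |
| 2% | 22% |
| 5% | 46% |
| 10% | 72% |

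The chance reaches one half at p = 1 − 0.5^(1/12) ≈ 5.6%. These are chances of a trigger, not of a missing tracing.

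**The case against.** **The rule may not apply at Visit 10.** The active treatment phase is not defined, and an instruction to stop drug most naturally addresses someone with treatment left. Central reading may also return the result after treatment has ended, and a site could then simply proceed to Visit 11. This stands as an ambiguity. The synopsis puts Visit 10 inside the treatment period, which supports the reading used here. On the other reading the rule could never act on a scheduled ECG.

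**Existing safeguards cover most of the gap.** A clinically significant finding must be reported as an AE, and if related it must be followed to resolution or stability, which can hardly be judged for an ECG finding without another ECG. This largely stands. A reader might infer that the flagged subject has nothing but the efforts clause, or that the Week 28 tracing is forbidden or lost. The documents support neither inference: the tracing is possible but not secured.

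**Week 28 is not essential.** At a 9-hour half-life, five half-lives is 45 hours, so an ECG a few days after Visit 10 might already be off drug. This is fair, subject to the same assumption about topical use. It does not help if the last-day assessments are done on the day of Visit 10, and nothing in the text prevents that.

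**Withdrawal is a cautious choice in a 12-subject pilot.** Stopping drug is the cautious part, and the fix keeps it. Ending observation adds no protection.

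**Unscheduled ECGs can trigger the rule earlier,** when stopping drug has real effect. This is correct, so it would be wrong to infer that the rule has no use. The point is confined to scheduled tracings.

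**Conclusion.** The point holds, at minor severity. On scheduled ECGs, 8.2.3 ends no exposure that was not ending anyway, and it withdraws the flagged subject before the only scheduled off-drug tracing. Other sections partly protect this subject, but none requires or dates an off-drug ECG. The gap is widest for triggers not judged clinically significant and for AEs judged not related.

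The conclusion rests on reading Visit 10 as part of the active treatment phase, as the synopsis does. The event may not occur: the only clinical ECG evidence in the documents, from oral dosing of the prodrug in healthy volunteers (3.1), showed no clinically significant findings. It would be a mistake to read the 11% to 72% range as the risk of losing the tracing. The rates are assumed, and a loss would also require the 5.6 efforts and the AE follow-up to yield no off-drug ECG. The efficacy endpoint is measured at Visit 10 and is not affected.

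**What to change.** Amend 8.2.3 along these lines: *a subject who meets any of these ECG criteria permanently stops study medication but is not withdrawn from the study for that reason; a subject who meets a criterion at Visit 10 completes Visit 11, including the ECG.*

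The cost is one sentence of protocol text. The drug stop is unchanged, no visit or procedure is added for a Visit 10 trigger, and subjects remain free to withdraw.

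Optionally, the sponsor could cover an earlier trigger on a for-cause ECG in the same way, with an ECG and the Visit 11 safety assessments about 4 weeks after the last application. That would need a matching exception in 6.6.8, which removes a subject who cannot apply drug twice daily for more than 4 days in a row, and at most one rescheduled visit. It goes beyond the scheduled-ECG problem shown here.

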## 8.2.4. Study Medication Interruption and Discontinuation

### 8.2.4.1 Study Medication Interruption

Treatment with ATI-50002 Topical Solution should be temporarily interrupted in the event of severe adverse events considered related to ATI-50002, or in the event of one or more of the abnormal laboratory values in Table 1.

**Table 1: Study Medication Interruption Criteria**

Laboratory Test	Interrupt Study Medication if:	Resume Study Medication if:
WBC count	< 2 x 10  /L	≥ 2.5 x 10  /L
ANC	< 1 x 10  /L	≥ 1.5 x 10  /L
Lymphocyte count	< 0.5 x 10  /L	≥ 0.75 x 10  /L
Platelet count	< 75 x 10  /L	≥ 100 x 10  /L
Hemoglobin	< 8 g/dL or decrease > 2 g/dL	≥ 10 g/dL
AST or ALT	> 3 x ULN	< 2 x ULN or within 20% of baseline values
Serum creatinine	>2 x ULN	<1.5 x ULN or within 10% of baseline value

If a subject has one or more of the abnormal laboratory values noted in Table 1, the investigator or designee upon receipt and review of the central laboratory report should instruct the subject to interrupt study medication applications. The investigator or designee should ask the subject about symptoms, concomitant illnesses and medications and repeat the test(s) as soon as possible. The Medical Monitor must be notified of dose interruptions due to SAEs considered related to study medication or laboratory abnormalities noted in Table 1.

If the retest confirms the abnormal laboratory value, then the study medication interruption should continue, followed by repeat testing once a week or sooner at the discretion of the investigator. The subject should be followed until the laboratory abnormality(s) return to normal or to baseline values. Application of study medication may be resumed upon resolution of the abnormal laboratory values to the levels specified in Table 1 above.

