#### **6.6.8. Dose modification**

Subjects should not modify the study medication application procedure or frequency without the investigator's prior approval. All application modifications must be reported on the appropriate eCRF. If any meaningful study medication intolerance or safety issue occurs, after consulting with the Aclaris Therapeutics, Inc. Medical Monitor (see page 1), the investigator or designee may direct the subject to modify the study medication application frequency. If the subject cannot perform the twice-daily application frequency to the affected eyebrow(s) for more than 4 consecutive days, the subject must be removed from the study.

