### **8.2.4.2 Study Medication Discontinuation**

Study medication should be permanently discontinued in the event of any of the following:

- Severe infection requiring parenteral antimicrobial therapy or hospitalization
- Symptomatic herpes zoster
- Malignancy – except for non-melanoma skin cancer (e.g., squamous or basal cell carcinoma) not in or near the treatment area
- Anaphylactic or severe allergic reaction
- WBC Count:  $< 1 \times 10^9/L$  or second occurrence of  $< 2 \times 10^9/L$
- ANC:  $< 0.5 \times 10^9/L$  or second occurrence of  $< 1 \times 10^9/L$
- Lymphocyte count:  $< 0.3 \times 10^9/L$  or second occurrence of  $< 0.5 \times 10^9/L$
- Platelet count:  $< 50 \times 10^9/L$  or second event of  $< 75 \times 10^9/L$  - in each case, value should be confirmed by retesting before treatment discontinuation
- Hemoglobin:  $< 6.5 \text{ g/dL}$  or second occurrence of  $< 8 \text{ g/dL}$  - in each case, value should be confirmed by retesting before treatment discontinuation
- AST or ALT:
  - $> 5 \times \text{ULN}$  persisting for 1 week of study medication interruption or second event of  $> 5 \times \text{ULN}$
  - $> 3 \times \text{ULN}$  with total bilirubin  $> 2 \times \text{ULN}$  or symptoms of hepatocellular injury [fatigue, nausea, vomiting, right upper quadrant pain or tenderness, fever, rash and/ or eosinophilia ( $> 5\%$ )].
- Serum creatinine:  $> 2 \times \text{ULN}$  persisting for  $> 2$  weeks of treatment discontinuation or second occurrence of  $> 2 \times \text{ULN}$

The continued treatment of subjects who experience other serious or severe adverse events considered related to study treatment should be discussed with the Sponsor's medical monitor.

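### Table 1, hemoglobin row: for a reference value above 12 g/dL, a fall of more than 2 g/dL can meet the interrupt and the resume rule at once, and the reference sample is not named

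*Combined protocol and SAP*

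**What the plan says.** Section 8.2.4.1 calls for a temporary hold when any Table 1 laboratory limit is crossed. For hemoglobin the interrupt cell reads "< 8 g/dL or decrease > 2 g/dL". The resume cell gives one absolute level, 10 g/dL or more, with no condition on the size of the fall.

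The text below the table asks the site to interrupt, look for causes and retest promptly. It then says: "If the retest confirms the abnormal laboratory value, then the study medication interruption should continue". While the hold lasts, further tests are due weekly, or earlier if the investigator so decides. A separate sentence has the subject followed until the value is normal or back at baseline. The sentence on restarting drug is: "Application of study medication may be resumed upon resolution of the abnormal laboratory values to the levels specified in Table 1 above".

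Section 8.2.4.2 stops drug permanently for hemoglobin below 6.5 g/dL or a second value below 8 g/dL, and adds that the "value should be confirmed by retesting before treatment discontinuation". It has no line for a fall from a reference value.

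On the reference: the AST/ALT and creatinine resume cells name baseline, while the hemoglobin row names nothing. In section 8.2.3 the QTc change rule does name its reference: "an increase in the QTcF interval >60ms from Visit 1". Under sections 6.3.2 and 7.2.4, blood is drawn before the first application at both Visit 1 and Visit 2, and again at Visits 7, 10 and 11.

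**The concern.** A hold rule needs a matching release rule. Here the second trigger, a fall of more than 2 g/dL, has no release level of its own, so the release level for the first trigger applies by default. For anyone who starts above 12 g/dL, that level can already be met on the day the hold begins.

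Take a subject who falls from 14.5 to 11.5 g/dL, confirmed on retest. One sentence says that the hold goes on. Another says that drug may restart at a level which 11.5 already meets. Two sites, or two subjects at one site, could be handled differently under the same protocol.

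The unnamed reference adds a smaller uncertainty. With two pre-dose samples, one on-treatment value can count as a trigger against one sample and not against the other. What is at stake is consistent safety handling, not an efficacy result.

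**Working it through.** The plan gives no computed figure to reproduce here, and section 10.2 states that no power calculation is made. The check is a direct comparison of the two columns.

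**Inputs, all from Table 1.** Interrupt if Hb < 8, or if B − Hb > 2, which is Hb < B − 2. Resume if Hb ≥ 10. B is the reference hemoglobin. The documents give no baseline values, so B is varied.

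**Overlap.** Both columns hold when 10 ≤ Hb < B − 2. The width is (B − 2) − 10 = B − 12, which is positive only if B > 12. Listing values in steps of 0.1 g/dL for B from 6.0 to 20.0 gives exactly this set, and nothing at B ≤ 12.

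| B (g/dL) | Decrease limb interrupts below | Values meeting both columns | Width |
|---|---|---|---|
| 12 | 10.0 | none | 0 |
| 13 | 11.0 | 10.0 to <11.0 | 1.0 |
| 14 | 12.0 | 10.0 to <12.0 | 2.0 |
| 14.5 | 12.5 | 10.0 to <12.5 | 2.5 |
| 15 | 13.0 | 10.0 to <13.0 | 3.0 |
| 16 | 14.0 | 10.0 to <14.0 | 4.0 |

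In the example, 14.5 − 11.5 = 3.0 > 2 (interrupt), and 11.5 ≥ 10 (resume). At the resume level of 10, a subject with B = 14 is still 4.0 g/dL below reference, twice the fall that starts the hold.

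**Comparison with the other rows (resume level minus interrupt level).**
- WBC: 2.5 − 2 = 0.5 × 10⁹/L.
- ANC: 1.5 − 1 = 0.5 × 10⁹/L.
- Lymphocytes: 0.75 − 0.5 = 0.25 × 10⁹/L.
- Platelets: 100 − 75 = 25 × 10⁹/L.
- Hemoglobin, absolute limb: 10 − 8 = 2 g/dL.
- Hemoglobin, decrease limb: 10 − (B − 2) = 12 − B, which is −2 at B = 14.
- AST/ALT and creatinine can overlap only through their baseline option, at a baseline above 3/1.2 = 2.5 × ULN or above 2/1.1 ≈ 1.82 × ULN.

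The hemoglobin overlap needs only B > 12.

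**Does other text settle it?** The sentence on return to normal or baseline governs follow-up, not restarting. Section 8.2.4.2 has no decrease limb, so Table 1 is the only numeric rule for a fall that ends at 8 g/dL or more.

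**Reference sample (assumed values).** With Visit 1 = 14.0, Visit 2 = 13.2 and an on-treatment value of 11.5, the fall is 2.5 from Visit 1 (interrupt) but 1.7 from Visit 2 (no interruption).

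**The case against.** The best case for the plan is that its sentences can be read together. Resumption is permissive, and it depends on resolution of the abnormal value. A confirmed fall of more than 2 g/dL is itself a Table 1 abnormality, so a careful site could treat it as unresolved until it reverses, and then also require 10 g/dL. That reading is available and weakens the point. It does not remove it, because the only level that the table specifies is 10, which the value already meets.

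A reader might infer that the decrease limb fails altogether as a stopping rule. The documents do not support that. A fall of more than 2 g/dL still brings a hold, questions on symptoms and concomitant illness, a prompt retest and mandatory notice to the Medical Monitor. Section 7.2 adds monthly safety review and an independent safety monitor. The defect lies in when the hold ends.

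A reader might also infer that the reference sample is indeterminable. It is not. The protocol calls Visit 2 Baseline throughout, and 8.2.4.1 uses baseline as its comparator elsewhere. The QTc rule names Visit 1 where Visit 1 is meant, which can be read in favour of Visit 2 here. What stands is that the row should say so.

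Exposure is also narrow. Scheduled on-treatment samples fall at Visits 7 and 10, and all medication is collected at Visit 10, so restarting can follow only the Visit 7 sample or an unscheduled test. A Visit 2 result reported after the first application matters only if the fall is counted from Visit 1.

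Finally, an absolute floor of 10 g/dL after work-up could be a deliberate clinical choice. If so, the row should state that it also releases a hold for a fall.

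**Conclusion.** The point holds as an ambiguity in one row of a safety table. For B above 12 g/dL, hemoglobin from 10 to below B − 2 satisfies both columns, over a width of B − 12 g/dL. This follows from the printed limits and needs no assumption beyond the value of B. How often it would arise cannot be derived, since no baseline hemoglobin is given and a fall of more than 2 g/dL must occur first. With about 12 subjects and essentially one scheduled sample at risk, it may never arise. It is a desirable wording correction, with no claimed effect on any efficacy summary.

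Two wider readings should not be attached to it. Exclusion criterion 13 admits platelet counts below the Table 1 hold level, but entry and hold limits need not match, and such a candidate must still be judged free of clinically significant abnormality and remains subject to Table 1. Section 6.6.8, under which a subject who cannot apply drug twice daily "for more than 4 consecutive days, the subject must be removed from the study", raises the question of whether safety holds count. That question touches every Table 1 row and is separate from this one.

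**What to change.** Reword the hemoglobin row of Table 1:

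- *Interrupt if:* below 8 g/dL, or a decrease of more than 2 g/dL from the Visit 2 pre-dose value.
- *Resume if:* 10 g/dL or more, and no more than 2 g/dL below the Visit 2 pre-dose value.

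The interrupt level becomes the larger of 8 and B − 2, and the resume level the larger of 10 and B − 2. No value then meets both columns for any B. The resume level is 10 at B = 12, 12 at B = 14 and 14 at B = 16. At B = 14.5 it is 12.5, so the subject at 11.5 stays on hold.

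The change removes the contradiction but does not create a margin. For B of 12 or more, both levels equal B − 2, so a small fluctuation could start or end a hold. If the sponsor wants a gap like that in the count rows, it can set a smaller permitted shortfall for resuming; its size is a clinical decision.

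The cost is the wording of one row, with no new samples or visits. The downside is that some hemoglobin holds will last longer than under a plain level of 10 g/dL.
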